2.4 Sample Size

As stated in Introduction the dosing of IMP stopped earlier than planned. Hence, the sample size assumptions originally stated in the protocols do not longer hold. In POLAR-A a total of n=301 patients have been randomised as compared to the planned n=280, and in POLAR-M n=290 patients have been randomised as compared to the planned n=420. The sample size protocol text below are stated for reference.

Protocol text (Section 10.2 in the CSPs)

The assumption of the proportion of patients who will satisfy the criteria for the primary endpoint in the untreated (placebo) study population is based on the results in the SCOT trial. Results were presented at ASCO 2017 and roughly 40% of the placebo population had symptoms graded “quite a bit/very much”, which corresponds to 3 or more in this study.

With 112 patients per group, the **POLAR-A** study has 91% power to detect a reduction (improvement) from 40% to 20% (OR = 0.375) in the primary endpoint using two-sided test controlled at the 0.05 type-I error rate. To account for 20% dropout in the study, in total 280 patients (140 patients per arm) will be randomised.

With 112 patients per group, the **POLAR-M** study has 91% power to detect a reduction (improvement) from 40% to 20% (odds ratio = 0.375) in the primary endpoint using two-sided test controlled at the 0.05 type-I error rate. To account for 20% dropout in the study, in total 420 patients (140 patients per arm) will be randomised.

Sample size assumptions will be monitored in a blinded fashion as part of the regular monitoring of the study. In case there are indications these are not met; a re-estimation of the sample size may occur.

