2.5 Changes From the Protocol Planned Analysis

Premature stop of administration of IMP in both POLAR-A and POLAR-M as well as the premature stop of recruitment in POLAR-M has several implications for the statistical analyses and the evaluation of the study data:

- Primary analysis. The Cochran-Mantel-Haenszel method described in the protocols has been fully specified to also include adjustment for cumulative oxaliplatin exposure. This amounts to replacing N, the number of subjects, in the divisor of the event rate calculation with cumulative oxaliplatin exposure. Also, in the protocols the CMH approach also adjust for FACT/GOG at baseline, but since there were very few patients with CIPN at baseline the primary analysis described in Section 5.1.1. does not include FACT/GOG at baseline.
- A negative binomial model will also be applied to the primary endpoint data as a supportive or exploratory analysis.
- Earlier stop of recruitment in POLAR-M has resulted in actual n=290 randomised patients as compared to the planned n=420.
- The primary analysis will be on the combined dataset including both POLAR-A and POLAR-M where study will be used as a stratification factor in all statistical analyses. Both studies will also be reported separately (see details in Section 3).
- Due to the lack of exposure of IMP a modified ITT (mITT) analysis set has been defined that will replace the Full Analysis Set (FAS). See further details in Section 3.1.
- Statistical analyses and summary tables will include data up to 12 months after the first dose of IMP (Assessment Visit 4). Data that has been collected after Assessment Visit 4 will only be included in the listings by patient.

Miscellaneous changes from the protocol planned analyses:

- The endpoint “mean health index using the FACT/GOG” as stated in the protocols will not be analysed.
- The variable Body Temperature although specified in vital signs section of the protocol has not been collected in the studies.
- In the CSP it says “PledOx Toxicities” but has been re-defined here in the SAP as “IMP Toxicities” since that is the way the data is collected and reported.

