3.2 Hypothesis to be Tested

With respect to the primary endpoint Moderate to Severe CIPN at 9 months after first dose of IMP the statistical hypothesis to test is:

$$H_0: \mu_{5\mu\text{mol/kg}} = \mu_{\text{placebo}}$$

$$H_1: \mu_{5\mu\text{mol/kg}} \neq \mu_{\text{placebo}}$$

where μ_x represents the oxaliplatin-dose adjusted Moderate to Severe CIPN event rate at 9 months on treatment x . The treatment effect will be captured as the ratio of event rates, $\Psi = \mu_{5\mu\text{mol/kg}} / \mu_{\text{placebo}}$, so that the preceding null and alternative hypotheses can be reframed as

$$H_0: \Psi = 1 \text{ versus } H_1: \Psi \neq 1$$

A rate ratio <1 favours the PledOx 5µmol/kg group over placebo.

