5.1 Primary Endpoint

5.1.1 Moderate to Severe CIPN

The primary endpoint is defined as the proportion of patients (with moderate or severe chronic CIPN) scoring 3 or 4 in at least 1 of the first 4 items of the FACT/GOG-NTX-13 (i.e., FACT/GOG-NTX-4), targeting numbness, tingling or discomfort in hands and/or feet, 9 months after the first dose of IMP (i.e. PledOx or placebo administered on Day 1, Cycle 1 of mFOLFOX6 chemotherapy).

Baseline is defined as the time of administration of the first dose of IMP (Day 1, Cycle 1).

Moderate to Severe CIPN will derived (SAS) as follows:

```
cipn=0;  
IF ntx1_std=. AND ntx2_std=. AND ntx3_std=. AND ntx4_std=. THEN cipn=.;  
ELSE IF ntx1_std IN('3','4') OR ntx2_std IN('3','4') OR  
      ntx3_std IN('3','4') OR ntx4_std IN('3','4') THEN cipn=1;
```

Primary Analysis – Cochran-Mantel-Haenszel. The primary analysis of the primary endpoint Moderate to Severe CIPN (yes/no) at 9 months after first dose of IMP will be analysed by the Cochran-Mantel-Haenszel (CMH) estimate of the common relative risk of Moderate to Severe CIPN. The treatment effect will be assessed by estimating the ratio of the incidence rates of CIPN in PledOx 5µmol/kg versus Placebo along with its 95% confidence interval and corresponding p-value. The CMH estimate will be adjusted for cumulative exposure of oxaliplatin and stratified by study and region. Incidence rates (95% CIs) for each treatment will also be presented.

Notations. The combined analysis includes two studies (POLAR-A and POLAR-M) and two geographical regions (Asia/Non-Asia), and so there are 4 strata, where

- 1 = POLAR-A / Asia
- 2 = POLAR-A / Non-Asia
- 3 = POLAR-M / Asia
- 4 = POLAR-M / Non-Asia

Treatments are denoted by 1 and 2, where 1 = PledOx 5µmol/kg and 2 = Placebo. For treatment j in the i^{th} strata the cumulative exposure of oxaliplatin is T_{ij} and E_{ij} is CIPN events. Let $T_{i\bullet} = T_{i1} + T_{i2}$ and $E_{i\bullet} = E_{i1} + E_{i2}$ denote total cumulative exposure of oxaliplatin and total CIPN events in the i^{th} strata.

CMH point estimate of the common relative risk across strata. Under $H_0: R_1 = R_2 = R$, Breslow and Day [1] provide the stratified Cochran-Mantel-Haenszel estimate of the common relative risk as

$$\hat{R}_{M-H} = \frac{\sum_{i=1}^k \frac{E_{i1}T_{i2}}{T_{i\bullet}}}{\sum_{i=1}^k \frac{E_{i2}T_{i1}}{T_{i\bullet}}}$$

Also, Robins, Breslow and Greenland [2] provide an estimate of the variance of $\log \hat{R}_{M-H}$ as

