$$\hat{V}[\log(\hat{R}_{M-H})] = \frac{\sum_{i=1}^k \frac{T_{i1} T_{i2} E_{i\bullet}}{T_{i\bullet}^2}}{\hat{R}_{M-H} \left\{ \sum_{i=1}^k \frac{T_{i1} T_{i2} E_{i\bullet}}{T_{i\bullet} (T_{i2} + T_{i1} \hat{R}_{M-H})} \right\}^2}$$

Then, a 95% confidence interval for the common relative risk across strata is,

$$\exp \{ \log(\hat{R}_{M-H}) \pm 1.96 \times SE \}$$

where $SE = \sqrt{\hat{V}[\log(\hat{R}_{M-H})]}$.

The statistic $Z = \frac{\log(\hat{R}_{M-H})}{SE} \sim N(0,1)$ so the 2-sided p-value is calculated by $2 \times (1 - CDF(|z|))$.

CMH event rates for each treatment. The Cochran-Mantel-Haenszel oxaliplatin exposure weighted incidence rate estimate for treatment j across strata is given by

$$U_j = \frac{\sum_{i=1}^k w_i \lambda_{ij}}{\sum_{i=1}^k w_i}, \quad j=1,2 \quad \text{and} \quad \lambda_{ij} = \frac{E_{ij}}{T_{ij}} \quad (\text{i.e the event rate for treatment } j \text{ in strata } i) \text{ and}$$

$$w_i = \frac{2}{\frac{1}{T_{i1}} + \frac{1}{T_{i2}}} \quad (\text{i.e. the harmonic mean cumulative exposure of oxaliplatin in strata } i).$$

CMH variance of the event rates. The variance of Cochran-Mantel-Haenszel oxaliplatin exposure weighted incidence rate estimate for treatment j across strata is given by

$$\text{Var}[U_j] = \text{Var} \left[\frac{\sum_{i=1}^k w_i \lambda_{ij}}{\sum_{i=1}^k w_i} \right] = \frac{\sum_{i=1}^k w_i^2 \text{Var}(\lambda_{ij})}{\left(\sum_{i=1}^k w_i \right)^2}$$

and hence

$$\hat{\text{Var}}[U_j] = \frac{\sum_{i=1}^k w_i^2 \text{Var}(\hat{\lambda}_{ij})}{\left(\sum_{i=1}^k w_i \right)^2} = \frac{\sum_{i=1}^k w_i^2 \frac{\hat{\lambda}_{ij}^2}{E_{ij}}}{\left(\sum_{i=1}^k w_i \right)^2} = \frac{\sum_{i=1}^k w_i^2 \frac{E_{ij}}{T_{ij}^2}}{\left(\sum_{i=1}^k w_i \right)^2}$$

Further,

$$\text{Var}[\log(U_j)] = \frac{1}{U_j^2} \text{Var}[U_j] = \frac{\left(\sum_{i=1}^k w_i \right)^2}{\left(\sum_{i=1}^k w_i \lambda_{ij} \right)^2} \times \frac{\sum_{i=1}^k w_i^2 \text{Var}(\lambda_{ij})}{\left(\sum_{i=1}^k w_i \right)^2} = \frac{\sum_{i=1}^k w_i^2 \text{Var}(\lambda_{ij})}{\left(\sum_{i=1}^k w_i \lambda_{ij} \right)^2}$$

and so

$$\hat{\text{Var}}[\log(U_j)] = \frac{\sum_{i=1}^k w_i^2 \text{Var}(\hat{\lambda}_{ij})}{\left(\sum_{i=1}^k w_i \hat{\lambda}_{ij}\right)^2} = \frac{\sum_{i=1}^k w_i^2 \frac{\hat{\lambda}_{ij}^2}{E_{ij}}}{\left(\sum_{i=1}^k w_i \hat{\lambda}_{ij}\right)^2} = \frac{\sum_{i=1}^k w_i^2 \frac{E_{ij}}{T_{ij}^2}}{\left(\sum_{i=1}^k w_i \frac{E_{ij}}{T_{ij}}\right)^2}$$

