Then, a 95% confidence interval for the Cochran-Mantel-Haenszel oxaliplatin exposure weighted incidence rate estimate across strata is,

$$U_j \times \exp \left\{ \pm 1.96 \sqrt{\widehat{\text{Var}}[\log(U_j)]} \right\}$$

Interpretation of parameter estimates. The Cochran-Mantel-Haenszel method provide estimates of oxaliplatin-dose adjusted Moderate to Severe CIPN event rates at 9 months. The associated unit of measurement for the CMH estimates is therefore the CIPN event rate per unit dose of oxaliplatin. To aid in clinical interpretation and understanding, the CMH estimates will be scaled to a relevant clinical dose eg 800 mg/m² to allow the event rate to be expressed per 100 patients relative to this dose. It can also be used to represent the number of events saved when receiving active treatment as compared to placebo. The example data below illustrates this in more detail.

The exact same interpretation can be done for the event rates (LSmeans) estimated from the negative binomial model as described further below.

Table 2 Example data

	Placebo	PledOx 5 µmol/kg	
No CIPN	70 (59%)	86 (73%)	156
CIPN	48 (41%)	32 (27%)	80
	118	118	236

Table 3 Example data: Cochran-Mantel-Haenszel estimates of Moderate to severe CIPN 9 months after first dose of IMP

	N	Estimate	95% CI	P-value
PledOx 5 µmol/kg	118	0.000317	[0.000222; 0.000454]	-
Placebo	118	0.000462	[0.000343; 0.000623]	-
PledOx 5 µmol/kg vs Placebo	236	0.6869	[0.4391; 1.0745]	0.0999

Suppose the mean cumulative dose overall of oxaliplatin is 800 mg/m² so the event rates are estimated by:

PledOx 5 µmol/kg 0.000317 x 800 = 0.25 CIPN events per patient per 800 mg/m² of oxaliplatin

Placebo 0.000462 x 800 = 0.37 CIPN events per patient per 800 mg/m² of oxaliplatin

This translates into:

PledOx 5 µmol/kg 25 CIPN events per 100 patients treated

Placebo 37 CIPN events per 100 patients treated

This represents a saving of 12 CIPN events per 100 patients treated with PledOx 5 µmol/kg.

In the results presentation of the CSR the observed mean cumulative dose of oxaliplatin will be used.

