5.3 Secondary Efficacy Endpoints

5.3.1 Mild to Severe CIPN

Proportion of patients (with mild, moderate or severe chronic CIPN) scoring 2, 3, or 4, in at least 1 of the first 4 items of the FACT/GOG-NTX-13 (i.e. FACT/GOG-NTX-4), targeting numbness, tingling or discomfort in hands and/or feet, 9 months after the first dose of IMP.

Baseline is defined as the time of administration of the first dose of IMP (Day 1, Cycle 1).

Mild to Severe CIPN will derived (SAS) as follows:

```
cipn2=0;  
IF ntx1_std=. AND ntx2_std=. AND ntx3_std=. AND ntx4_std=. THEN cipn2=.;  
ELSE IF ntx1_std IN('2','3','4') OR ntx2_std IN('2','3','4') OR  
      ntx3_std IN('2','3','4') OR ntx4_std IN('2','3','4') THEN cipn2=1;
```

Mild to Severe CIPN will be analysed using the method of Cochran-Mantel-Haenszel as described in detail in Section 5.1.1.

Data Presentations

- Table: the analysis of Mild to Severe CIPN based on the negative binomial regression model will be presented by number of patients (N), treatment estimates and its 95% CIs. The rate ratio between PledOx 5 $\mu\text{mol/kg}$ and Placebo will be presented by the estimate, 95% CI and p-value.
- Table: the number and percentage of patients with Mild to Severe CIPN along with its 95% CI presented by treatment group and total for each treatment visit/assessment visit. The confidence intervals will be based on the method of Clopper-Pearson (exact).
- Figure: the proportion (including 95% CIs) of patients with Mild to Severe CIPN will be graphically depicted (lineplot) vs treatment cycle/assessment visit by treatment group.
- All observed values of Mild to Severe CIPN will be listed by patient.

All the analyses of Mild to Severe CIPN will be based on the observed cases. Hence, no imputation of missing values will be done.

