5.3.7 Long-term Moderate to Severe CIPN

Long-term Moderate to Severe CIPN is defined as the proportion of patients scoring 3 or 4 in at least 1 of the first 4 items of the FACT/GOG-NTX-13 (i.e. FACT/GOG-NTX-4), targeting numbness, tingling or discomfort in hands and/or feet 12 months after the first dose of IMP.

Baseline is defined as the time of administration of the first dose of IMP (Day 1, Cycle 1).

Moderate to Severe CIPN will derived (SAS) as follows (same as primary endpoint):

```
cipn=0;  
IF ntx1_std=. AND ntx2_std=. AND ntx3_std=. AND ntx4_std=. THEN cipn=.;  
ELSE IF ntx1_std IN('3','4') OR ntx2_std IN('3','4') OR  
      ntx3_std IN('3','4') OR ntx4_std IN('3','4') THEN cipn=1;
```

Long-term Moderate to Severe CIPN will be analysed using the method of Cochran-Mantel-Haenszel as described in detail in Section 5.1.1.

All the analyses of Long-term Moderate to Severe CIPN will be based on observed cases. Hence, no imputation of missing values will be done.

Data Presentations

- Table: the analysis of Long-term Moderate to Severe CIPN based on the negative binomial regression model will be presented by number of patients (N), treatment estimates and its 95% CIs. The rate ratio between PledOx 5 µmol/kg and Placebo will be presented by the estimate, 95% CI and p-value.

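### The primary CMH analysis gives a yes/no endpoint a Poisson person-time variance, so its confidence interval is too wide and the nominal 5% test runs at about 1–3%

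*SAP*

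**What the plan says.** The primary endpoint (Section 5.1.1) is a status at one visit. The SAS derivation sets it to 0 or 1 for each patient, and the analysis sentence reads "Moderate to Severe CIPN (yes/no) at 9 months after first dose of IMP will be analysed by the Cochran-Mantel-Haenszel (CMH) estimate". Section 2.5 explains the dose adjustment as "replacing N, the number of subjects, in the divisor of the event rate calculation with cumulative oxaliplatin exposure", and Section 3.2 defines the tested parameter as the "oxaliplatin-dose adjusted Moderate to Severe CIPN event rate at 9 months".

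Section 5.1.1 then gives a variance for the log of the Mantel-Haenszel ratio, built from E (events) and T (summed oxaliplatin dose) by stratum and arm. Under "CMH variance of the event rates" it gives each arm-by-stratum rate a variance of E/T². No patient count appears in either formula. The CI and the two-sided p-value come from this SE. Table 3 illustrates the method on example data: ratio 0.6869, 95% CI "0.4391; 1.0745", p = 0.0999.

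Two secondary endpoints use the same method: "Mild to Severe CIPN will be analysed using the method of Cochran-Mantel-Haenszel as described in detail in Section 5.1.1" (Section 5.3.1) and "Long-term Moderate to Severe CIPN will be analysed using the method of Cochran-Mantel-Haenszel" (Section 5.3.7).

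**The concern.** The formulas belong to person-time data, where events are counts accruing over exposure and the variance of a count equals its mean. Here each patient contributes one 0/1 result at month 9. Its variance is p(1 − p), not p, and at the risks the SAP works with (27% to 41% in the example) the factor 1 − p cannot be ignored. Putting dose in the denominator changes what is estimated. It does not turn a binary outcome into a Poisson count.

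This SE drives the one confirmatory p-value. By Section 3, POLAR-A alone is tested only if the combined test is significant, so lost power in the first step carries into the second. Section 1 explains that pooling was forced by halted dosing and by POLAR-M stopping at 290 of 420 patients, so there is little power to give away. The CIs for the ratio and for the arm rates also understate the precision of the data.

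**Working it through.** **Inputs.** From the SAP: 32/118 events on PledOx 5 µmol/kg and 48/118 on placebo (Table 2); ratio 0.6869, its CI and p (Table 3); two-sided 0.05 level (Sections 3 and 5.1.1); 112 per group, 40% vs 20% (Section 2.4). The SAP gives no dose distribution, so dose CVs, the dose–CIPN relation, stratum shares (15/45/10/30%) and the 200-per-arm case are assumptions.

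**1. What the variance reduces to.** With one stratum and E = E1 + E2, the formula is (T2 + T1·R)² / (R·T1·T2·E). Substituting R = E1·T2/(E2·T1) gives T2 + T1·R = T2·E/E2, and the expression becomes E/(E1·E2) = 1/E1 + 1/E2. Dose totals cancel and patient numbers never enter.

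**2. Reproducing Table 3.** √(1/32 + 1/48) = 0.2282. The printed CI implies ln(1.0745/0.4391)/3.92 = 0.2283. With ratio 0.6869 this SE gives CI 0.439–1.074 and p = 0.0998, against the printed 0.0999.

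**3. Binomial variance, same ratio, equal dose per patient.** √(1/32 − 1/118 + 1/48 − 1/118) = 0.1874. CI 0.476–0.992, p = 0.045. Variance ratio 0.05208/0.03513 = 1.48, so the SAP variance is 48% too large.

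**4. Crude ratio, no dose adjustment.** For 32/48 = 0.667, p = 0.076 with 0.2282 and p = 0.031 with 0.1874. This isolates the variance. Comparing Table 3 (p = 0.0999) with Table 4 (p = 0.0293) does not, because those rows also differ in dose adjustment and in rate ratio versus odds ratio.

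**5. Unequal dose.** Linearising log(E/T) adds a term per arm to the binomial variance. With n = 118 and the ratio held at 0.6869:

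| Dose–CIPN relation | Added per arm | p, CV 30% | p, CV 40% |
|---|---|---|---|
| Risk proportional to dose | −CV²/n | 0.0405 | 0.037 |
| Unrelated | +CV²/n | 0.0498 | 0.0535 |
| Risk falls as dose rises | +3CV²/n | 0.0595 | 0.071 |

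The SAP variance is about 20% to 60% too large over this range.

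**6. Size of the nominal 5% test.** Exact enumeration, 118 per arm, equal dose:

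| Common risk | SAP variance |
|---|---|
| 20% | 2.6% |
| 30% | 1.8% |
| 40% | 1.1% |

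Simulating the full four-stratum formula with dose CV 30–40% gives about 1–3% at 30–40% risk and about 2–4% at 20% risk. A patient-level sandwich SE gives about 4–5.6%.

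**7. Power.**

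| Setting | SAP variance | Corrected variance |
|---|---|---|
| 118/arm, 40.7% vs 27.1%, equal dose (exact) | 41% | 59% |
| 200/arm (assumed), 40% vs 26.7%, equal dose | 67% | 81% |
| Same, dose CV 30–40% | 62–67% | 70–83% |
| 112/arm, 40% vs 20%, equal dose (exact) | 83% | 91% |

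A normal approximation gives 80% vs 88% for the last row. That row is only an illustration, since Section 2.4 says "the sample size assumptions originally stated in the protocols do not longer hold".

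**The case against.** The strongest point is that the direction and size of the error depend on a dose distribution the SAP does not give. From step 5, the excess per arm is 1/n at equal dose, and an inverse dose–risk relation offsets it by 3CV²/n. The excess therefore vanishes at CV = √(1/3), about 58%. An inverse relation is plausible: patients with neuropathy may have oxaliplatin cut, and the mITT set can admit patients with little treatment. Simulations with that relation at CV 60% put the size at about 4–5%, and one at CV 70% gave 5.3%, within simulation error of 5%. So the conservatism is not unconditional. That does not rescue the formula, which would then be right only by coincidence.

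It can also be said that a conservative test harms no one, that Section 2.5 discloses the change of divisor, and that the SAP prints the less favourable Table 3 result beside Table 4. The first is true of type I error but not of power or of the reported precision. The disclosure covers the divisor only; nowhere does the SAP justify the variance. The other analyses of the primary endpoint do not repair it: negative binomial regression is also a count model and is supportive, while exact logistic regression respects the 0/1 outcome but is exploratory and not dose-adjusted.

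Finally, the power figures are illustrations. The SAP does not state the size of the combined mITT set, so the actual loss is unknown. This stands.

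**Conclusion.** The concern holds. The variance is mis-specified for a binary endpoint, and the SAP's own example shows that the choice can decide significance. With equal dose, or with dose CV up to 40% under the relations tried, the test is conservative: about 1–3% instead of 5% at 30–40% risk, with a power loss of 18 percentage points at the example's own numbers (59% − 41%). The conservatism shrinks as dose spread and an inverse dose–risk relation grow, and is roughly gone at a CV near 60%. No material type I error inflation appeared in any setting tried. This is a loss of efficiency and a misstatement of precision, not a route to a false claim. It should be fixed because it sits in the only confirmatory test and in the gate to POLAR-A.

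**What to change.** Keep the Mantel-Haenszel ratio, the arm rates U_j and the Section 3.2 hypothesis. Replace only the variance, and name one estimator. A patient-level sandwich for log(R) is suitable. With y = 0/1 outcome, d = patient dose, T_i = T_i1 + T_i2 and A_i = (E_i1 + R·E_i2)/T_i²:

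- PledOx patient in stratum i: (T_i2/T_i)·y − T_i2·A_i·d
- Placebo patient in stratum i: −R·(T_i1/T_i)·y + T_i1·A_i·d

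For each stratum and arm, take the number of patients times the sample variance of these contributions. Sum over strata and arms, and divide by (Σ E_i1·T_i2/T_i)². The square root is the SE of log(R).

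For the arm rates, treating the weights as fixed, replace E/T² by n_ij times the sample variance of (y − λ_ij·d), divided by T_ij². A bootstrap resampling patients within study, region and arm is an alternative. If preferred, the SAP must fix the replicates, the seed and the handling of sparse cells.

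Apply the same change in Sections 5.3.1 and 5.3.7 and rerun Table 3. The cost is SAP wording and a few lines of code before unblinding, with no new data and no change of estimand.

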Supportive Analysis of the primary endpoint - Negative Binomial Regression. A supportive analysis of the primary endpoint Moderate to Severe CIPN (yes/no) at 9 months after first dose of IMP will be analysed by a negative binomial regression model adjusted for study (POLAR-A / POLAR-M) and region (Asia / non-Asia). An offset variable will also be used to adjust for the oxaliplatin exposure defined as the logarithm of the cumulative dose of oxaliplatin received by each patient. Estimate of the treatment contrast (rate ratio) and its corresponding 95% confidence interval will be based on the anti-log of the model parameter estimate and CI.

SAS Code Example Negative Binomial Regression using PROC GENMOD

```
PROC GENMOD;
  CLASS study region trt;
  MODEL cipn = study region trt/DIST=negbin LINK=log SCALE=deviance OFFSET=log_exp;
  ESTIMATE 'PledOx 5 µmol/kg vs Placebo' trt 1 -1;
  LSMEANS trt / CL EXP;
RUN;
```

If convergence criterion is not met using PROC GENMOD an alternative using PROC NLMIXED will be used.

SAS Code Example Negative Binomial Regression using PROC NLMIXED

```
PROC NLMIXED;
  PARMs b0 -2 b1 .1 b2 -.01 b3 .1 phi .1;
  eta = log_exp + b0 + b1*(study=1) + b2*(region=1) + b3*(trt=0);
  mu = exp(eta);
  LL = y*log(phi*mu) - (y+(1/phi))*log(1+(phi*mu)) + lgamma(y+(1/phi)) -
lgamma(1/phi) - lgamma(y+1);
  MODEL y ~ general(LL);
RUN;
```

Exploratory Analysis – Exact Logistic Regression. An exploratory analysis of the primary endpoint Moderate to Severe CIPN at 9 months after first dose of IMP will be analysed by exact logistic regression model adjusted for study (POLAR-A / POLAR-M) and region (Asia / non-Asia). Estimate of the treatment effect and its corresponding 95% confidence interval will be based on the odds-ratio.

SAS Code Example Exact Logistic Regression

```
PROC LOGISTIC DESC;
  CLASS study region trt(ref='0: Placebo');
  MODEL cipn = study region trt;
  EXACT trt;
RUN;
```

Using the same example data presented above, a crude estimate of the odds-ratio then is:

$$(0.27/0.73) / (0.41/0.59) = 0.53$$

Table 4 Example data: Exact Logistic Regression of Moderate to severe CIPN 9 months after first dose of IMP

	N	CIPN (%)	Odds-ratio	95% CI	P-value
PledOx 5 µmol/kg	118	27.1	-	-	-
Placebo	118	40.7	-	-	-
PledOx 5 µmol/kg vs Placebo	236	-	0.54	[0.31;0.94]	0.0293

Data Presentations

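### Under the only coding the SAP gives for trt (0 = Placebo), both negative binomial code examples return placebo/PledOx, the reverse of the ratio defined in Section 3.2 (supportive analysis only)

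*SAP*

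**What the plan says.** Section 3.2 sets the direction: the effect is the PledOx 5 µmol/kg event rate divided by the placebo rate, and values below 1 favour PledOx. For the supportive analysis, Section 5.1.1 says the rate ratio and its interval "will be based on the anti-log of the model parameter estimate and CI". No change of sign is mentioned.

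The relevant code lines, all in Section 5.1.1, are:

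- PROC GENMOD, the planned program: "CLASS study region trt" with no reference or ordering option, then "ESTIMATE 'PledOx 5 µmol/kg vs Placebo' trt 1 -1".
- PROC NLMIXED, used only if GENMOD does not converge: "eta = log_exp + b0 + b1*(study=1) + b2*(region=1) + b3*(trt=0".
- PROC LOGISTIC, exploratory analysis: "CLASS study region trt(ref='0: Placebo". This is the only place where a treatment level is tied to the SAS variable `trt`.

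A second numbering appears under Notations for the CMH formulas: "Treatments are denoted by 1 and 2, where 1 = PledOx 5µmol/kg and 2 = Placebo".

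**The concern.** A program's contrast must match the ratio that the text defines. Here the direction of the reported ratio depends on how `trt` is coded, and the one coding shown for `trt` puts placebo at level 0. With that coding the GENMOD contrast runs from placebo to PledOx although its label says the opposite, and the NLMIXED indicator switches on for placebo. A supportive ratio read straight from either output would show a benefit as harm, or harm as benefit. The author set placebo as reference in the logistic example but not in GENMOD, which suggests an oversight rather than a choice. It is better settled before unblinding, because reversing a sign afterwards can look like a post-hoc change.

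**Working it through.** **Inputs.** Table 2: 32/118 events on PledOx and 48/118 on placebo. Table 3: rates of 0.000317 and 0.000462 per mg/m², ratio 0.6869 [0.4391; 1.0745], p = 0.0999. The SAP gives no worked negative binomial result, so Table 3 serves as the reference for direction.

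**Step 1: reproduce the SAP's example.**
- Ratio: 0.000317 / 0.000462 = 0.686 (stated 0.6869; the difference is rounding of the rates).
- SE from the stated interval: [ln(1.0745) − ln(0.4391)] / (2 × 1.96) = 0.2283. From the event counts: √(1/32 + 1/48) = 0.2282.
- The p-value from this ratio and SE is 0.0999, as stated.
- Table 4 odds ratio: (32/86) / (48/70) = 0.543 (stated 0.54).

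Both worked examples are therefore PledOx relative to placebo, as Section 3.2 requires.

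**Step 2: algebra of the two programs.**
- NLMIXED with 0 = placebo: for patients alike in study, region and exposure, η(placebo) − η(PledOx) = b3, so exp(b3) = placebo/PledOx.
- NLMIXED with 1 = PledOx, 2 = placebo: `(trt=0)` is never true. The treatment column is all zeros and b3 drops out of the likelihood.
- GENMOD: `trt 1 -1` is the first sorted level minus the second. With placebo at 0 this is placebo minus PledOx. With 1 = PledOx and 2 = placebo it is PledOx minus placebo.

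**Step 3: numerical check on the Table 2 counts.** Each patient was given the arm-mean exposure implied by Tables 2 and 3:
- PledOx: 32 / 0.000317 / 118 ≈ 855 mg/m²
- Placebo: 48 / 0.000462 / 118 ≈ 880 mg/m²

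Study and region were left out because the example has no such split. The SAP's NLMIXED log-likelihood was maximised with phi fixed at 0.001 and at 0.1. The GENMOD contrast was taken from a log-link Poisson fit with the same offset, since the direction does not depend on the dispersion.

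| Coding of `trt` | GENMOD, exp(contrast) | NLMIXED, exp(b3) |
|---|---|---|
| 0 = placebo (logistic example) | 1.457, inverted | 1.457 (b3 = 0.3767), inverted |
| 1 = PledOx, 2 = placebo (CMH index) | 0.686, correct | not estimable |

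In the non-estimable case the design has rank 1 instead of 2. Started at 0.1, 1 and −1, b3 stayed where it began with an identical minus log-likelihood (166.3359 at phi = 0.001). Only 0 = PledOx, which the SAP never states, gave 0.686 from NLMIXED.

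**Step 4: illustrative size.** Inverting Table 3: 1/0.6869 = 1.456, 1/1.0745 = 0.931, 1/0.4391 = 2.277. Only the sign of the log ratio changes, so |z| and the p-value do not.

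**The case against.** The case for leaving this alone has several parts.

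- **The coding is not formally specified.** Each snippet is headed as an example, none names a dataset, and GENMOD models `cipn` while NLMIXED models `y`. Carrying the logistic label over to the other two is an inference. This stands in part: a reader might infer that the supportive ratio will certainly be inverted, and the SAP does not fix that. With 1 = PledOx and 2 = placebo, the planned GENMOD program is correct.
- **The 1/2 numbering is a formula index.** It defines the subscript in the CMH formulas, not values of `trt`. This is fair, and it weakens the non-estimable branch. It also leaves 0 = placebo as the only coding shown for `trt`, and under that coding both programs invert.
- **NLMIXED is only a fallback and carries no label.** True. The misleading label belongs to GENMOD.
- **A reversal would be noticed.** Section 5.1.1 asks for the arm estimates beside the ratio, and GENMOD's LSMEANS supplies them, so a reversed ratio would contradict its own table and the CMH result. This stands for GENMOD. The NLMIXED snippet has no LSMEANS or ESTIMATE statement to offer that check.
- **The secondary endpoints are not clearly exposed.** A reader might infer that Mild to Severe CIPN (Section 5.3.1) and Long-term CIPN (Section 5.3.7) inherit the problem. Both sections name CMH as the method, and only their table bullets mention the negative binomial model. They are affected only if those tables follow the bullets.

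**Conclusion.** The code examples are wrong as written under the one coding the SAP shows for `trt`: both return placebo/PledOx where Section 3.2 requires PledOx/placebo. Under the only other numbering in the document, GENMOD is right and the NLMIXED effect cannot be estimated. Neither coding shown makes both programs correct, and the NLMIXED line fails under both.

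This concerns the supportive analysis. The primary CMH estimate comes from closed formulas and is untouched, as is the testing sequence in Section 3. An inversion leaves the p-value as it is. The change from 0.69 (0.44 to 1.07) to 1.46 (0.93 to 2.28) is the reciprocal of the CMH example and only illustrates the size; it is not a negative binomial result.

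The conclusion assumes that the model is fitted to the PledOx 5 µmol/kg and placebo arms only, that the 0 in the logistic label is the numeric value of `trt`, that the PledOx level sorts after it, and that GENMOD uses its default ascending order. It should be corrected, but it does not threaten the main conclusion of the trial.

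**What to change.** Make three short edits in Section 5.1.1:

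1. State one coding of `trt` for all snippets, for example 0 = Placebo and 1 = PledOx 5 µmol/kg, and say that the 1/2 numbering under Notations is only a formula index.
2. In GENMOD, set the level order or the reference explicitly and write the ESTIMATE as PledOx minus placebo, with coefficients matched to that order: `trt -1 1` if placebo is the first level, `trt 1 -1` if it is the last.
3. In NLMIXED, replace the last term with `b3*(trt=1)`, so that exp(b3) is PledOx/placebo.

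The cost is a few lines of text, with no new data or analysis and no effect on the primary analysis.
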